4.4.1.2. Secondary Efficacy Endpoints for the Induction Period

Secondary efficacy endpoints for the induction dosing period for participants who have not permanently discontinued at Week 12 and have achieved at Week 12 include clinical response, endoscopic remission, endoscopic response, symptomatic remission, symptomatic response, histologic remission, and histologic-endoscopic mucosal healing at Week 12.

Analyses will be performed as per the methodology described in Section 4.1.1.

The mITT population will be used for the secondary efficacy outcome analyses.

4.4.1.3. Secondary Efficacy Endpoints for the Maintenance Period

Secondary efficacy endpoints for the maintenance period for participants who were responder per IWRS at Week 12, have not permanently discontinued at Week 52, and have achieved at Week 52 include clinical remission, clinical response, endoscopic remission, endoscopic response, symptomatic remission, symptomatic response, histologic remission, and histologic-endoscopic mucosal healing at Week 52.

Analyses will be performed as per the methodology described in Section 4.1.1.

The mITT population will be used for the secondary efficacy outcome analyses.

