
 To evaluate the efficacy of induction treatment with LY3471851 compared to placebo with respect to clinical, endoscopic, and histologic improvement 	
Secondary comparisons of interest are the difference between LY3471851 and placebo in the proportion of participants who have not permanently discontinued at Week 12 and have achieved at Week 12:
 
 clinical response endoscopic remission endoscopic response symptomatic remission symptomatic response histologic remission histologic-endoscopic mucosal healing 
Secondary comparisons with binary endpoints will use a composite estimand as described for the primary comparison.

Objectives	Estimands/Endpoints

 To evaluate the efficacy of maintenance treatment with LY3471851 compared to placebo with respect to clinical, endoscopic, and histologic improvement 	
Secondary comparisons of interest include the difference between LY3471851 and placebo in the proportion of participants who were responders at Week 12 (Week 12 Responders) and have not permanently discontinued at Week 52, who at Week 52 still have
 
 clinical remission clinical response endoscopic remission endoscopic response symptomatic remission symptomatic response histologic remission histologic-endoscopic mucosal healing 
Secondary comparisons with binary endpoints will use a composite estimand as described for the primary comparison.

 To evaluate the efficacy of treatment with LY3471851 compared to placebo with respect to patient-reported outcomes and quality of life measures 	
Comparison of mean changes from baseline to Week 12 and to Week 52 in scores for
 
 IBDQ Urgency NRS Abdominal Pain NRS Nocturnal Stools Bristol Stool Scale PGR-S Fatigue NRS 
Secondary comparisons with continuous endpoints will use a hypothetical efficacy estimand strategy to address the intercurrent events of early discontinuation to assess the effect of study treatment in a hypothetical trial where all participants have complete data and continue to take study treatment without discontinuing from the study.

 To evaluate the PK of LY3471851 	
 Week 12 LY3471851 trough concentrations

Objectives	Estimands/Endpoints
	

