The secondary clinical question of interest is: What is the intervention difference in successful response rate of clinical response / endoscopic remission / endoscopic response / symptomatic remission / symptomatic response / histologic remission / histologic-endoscopic mucosal healing at Week 52 of intervention in patients with moderately to severely active UC, where successful response is defined as patient who achieves clinical response / endoscopic remission / endoscopic response / symptomatic remission / symptomatic response / histologic remission / histologic-endoscopic mucosal healing without discontinuing treatment, without increasing mandatory stable medications, and without taking prohibited medications prior to the time point of interest?

The estimand is described by the following attributes:

Population: patients with moderately to severely active UC who were responders at Week 12, have not permanently discontinued at Week 52, have achieved at Week 52. Further details can be found in Section 3.

Endpoint: clinical remission / clinical response / endoscopic remission / endoscopic response / symptomatic remission / symptomatic response / histologic remission / histologic-endoscopic mucosal healing at Week 52.

Treatment condition: the randomized treatment without rescue medication or change in background medication (treatment policy strategy). Further details on study interventions and concomitant, including rescue, interventions can be found in Section 6.

The 2 intercurrent events “intervention discontinuation for any reason” and “initiation of rescue intervention or change in background intervention “ are both addressed by the treatment condition of interest attribute. There are no remaining intercurrent events.

Population-level summary: difference in percentage of participants achieving clinical remission / clinical response / endoscopic remission / endoscopic response / symptomatic remission / symptomatic response / histologic remission / histologic-endoscopic mucosal healing at Week 52 between intervention conditions.

Rationale for estimand: The data collected after the treatment discontinuation or post-rescue medication will be categorized as nonresponder.

3) IBDQ / Urgency NRS / Abdominal Pain NRS / Nocturnal Stools / Bristol Stool Scale / PGR-S / Fatigue NRS

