The randomization ratios are described in Section 1.2.1.

Study Periods

This study has multiple periods.

Screening period

This period begins with Visit 1, which occurs 5 weeks (or less) before the planned randomization visit. A participant's screening evaluations must be completed and reviewed to confirm the participant's eligibility before randomization and dosing occurs at Visit 2.

Blinded induction and blinded maintenance periods

The double-blind, placebo-controlled, 12-week induction treatment period begins at Visit 2. Dosing, sample collection, and assessments continue Q2W, as shown in the SOA in the protocol. Between Week 12 and Week 14, based on samples and assessments collected at Week 12, participants will be classified as either "Week 12 Responders" or "Week 12 Nonresponders" based on the "clinical response" criteria defined in the protocol.

- "Week 12 Responders" will continue to receive their same randomly assigned treatment throughout the blinded 40-week Maintenance Period, with the final dose occurring at Week 50 and the last maintenance assessments and sample collections at Week 52.
- "Week 12 Nonresponders" will enter the Extension Induction and Extension Maintenance Periods.

Extension induction and maintenance periods

Beginning at Week 14, participants who were classified as Week 12 Nonresponders will receive the high dose (CC1 μg) of LY3471851 Q2W, unless a lower dose is selected for Stage 2 based on interim analyses.

Between Week 26 and Week 28, based on samples and assessments collected at Week 26, these participants will again be classified according to their clinical response status based on MMS (responder or nonresponder).

- Participants who are classified as responders based on the samples and assessments at Week 26 will continue to receive LY3471851 Q2W as maintenance through the remainder of the study. These participants have their final dose at Week 50 and their last maintenance assessments and sample collections at Week 52.
- Participants who are classified as nonresponders based on the Week 26 samples and assessments will be permanently discontinued from study drug when his/her status as a nonresponder has been determined; such participants will enter the post-treatment follow-up period.

Post-treatment follow-up period

[figure not shown]

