2.1. Multiplicity Adjustment

Multiplicity adjustment will not be employed in the analysis for this study.

3. Analysis Sets

Table KFAH.2 describes the populations planned for use in the analyses. The mITT population, as defined below, will be used in analyses of efficacy and PRO, unless otherwise noted in the SAP.

Table KFAH.2. Analysis Populations

Population	Description
ITT Population	All randomized participants. Participants will be analyzed according to the treatment to which they were assigned.
mITT Population	All randomized participants who receive at least 1 dose of study treatment (regardless of whether the participant fails to receive the correct treatment, or otherwise fails to follow the protocol). Participants will be analyzed according to the treatment to which they were assigned.
Safety Population	Same as mITT population
Pharmacokinetic Evaluable	All participants who receive at least 1 dose of investigational product and have sufficient blood sampling to allow for pharmacokinetic evaluation.

Abbreviations: GCP = Good Clinical Practice; ITT = intent-to-treat; mITT = modified intent-to-treat; SAP = statistical analysis plan.

Analyses of the maintenance dosing period and the extension periods will be based on the corresponding enrolled population as described in the table above.

4. Statistical Analyses

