4.1.2.1. Non-Responder Imputation (NRI)

The primary outcome is the proportion of patients with clinical remission at Week 12. For this and other categorical efficacy endpoints (for example, clinical remission (week 52), clinical response (week 12, 52), and endoscopic remission (week 12, 52)), non-responder imputation (NRI) will be used for missing clinical assessment values. Specifically, all patients who discontinue from the study at any time prior to week 12 for any reason or fail to have an adequate week 12 efficacy assessment will be considered a non-responder at week 12. Patients who discontinue from the study for any reason at any time prior to week 52 after having enrolled into the Maintenance Period or fail to have an adequate week 52 efficacy assessment, will be considered a non-responder at week 52.

The NRI may be applied at any time point specified for analysis.

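### The denominator of the eight Week 52 LY-versus-placebo comparisons is contradictory, and on its responders-only reading the comparison is not protected by randomisation

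*SAP*

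**What the plan says.** Randomisation happens once, at baseline (SAP Section 1.2.1). Under SAP Section 1.2, Week 12 responders "will continue to receive their same randomly assigned treatment throughout the blinded 40-week Maintenance Period", while "participants who were classified as Week 12 Nonresponders will receive the high dose" of LY from Week 14 unless a lower dose has been chosen. That includes nonresponders from the placebo arm.

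The Week 52 comparison is described in several places:

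- Protocol Section 3 frames it as the LY-placebo difference "in the proportion of participants who were responders at Week 12 (Week 12 Responders) and have not permanently discontinued at Week 52".
- SAP Section 1.1 gives the estimand population as patients "who were responders at Week 12, have not permanently discontinued at Week 52, have achieved at Week 52".
- SAP Section 3 says "Analyses of the maintenance dosing period and the extension periods will be based on the corresponding enrolled population".
- SAP Section 4.1.2.1 describes Week 52 non-responder imputation (NRI) for patients who leave "at any time prior to week 52 after having enrolled into the Maintenance Period".
- SAP Section 4.4.1.3 applies the endpoints "for participants who were responder per IWRS at Week 12, have not permanently discontinued at Week 52, and have achieved at Week 52", yet ends: "The mITT population will be used for the secondary efficacy outcome analyses".

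Section 4.4.1.3 sends all eight endpoints to SAP Section 4.1.1. There they receive CMH p-values, relative risks and confidence intervals for differences, stratified by three randomisation factors and region, all fixed at baseline.

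**The concern.** The denominator decides what the test means. If every mITT patient is counted, the arms being compared are those created by randomisation, apart from undosed patients. If only Week 12 responders are counted, they are not. A placebo responder improved without the drug; LY responders may also include people who respond only on the drug and have no counterpart among placebo responders. Stratifying on baseline factors does not restore comparability, and the plan has no principal-stratum estimand, sensitivity analysis or caveat for this selection.

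The result would be reported under the objective of maintenance efficacy against placebo, in a study meant to guide dose selection. As written, two programmers could produce different tables for the same endpoint.

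**Working it through.** **1. The plan's own figure.** The only stated power is for Week 12 remission: 89.5%, 94.5% and 96.5% for LY arms of 40, 60 and 80 against 40 on placebo, at 5% versus 35%. A two-sided arcsine approximation at alpha 0.05/3 gives 89.5%, 94.5% and 96.5%, so it reproduces. It says nothing about Week 52; the documents give no rate, size or power for that comparison.

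**2. The passages side by side.**

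- *Responders only:* Protocol Section 3; SAP Section 1.1 (second secondary estimand); SAP Section 3; the Week 52 NRI rule in SAP Section 4.1.2.1.
- *All mITT:* the closing sentence of SAP Section 4.4.1.3, and the general statements in Protocol Section 9.4.1 and SAP Section 4.1.
- *Literal reading of SAP Sections 1.1 and 4.4.1.3:* patients must also still be on treatment and have met the endpoint at Week 52. Every patient in such a denominator is a success, so each arm's rate is 100%. It also removes the discontinuers whom NRI counts as failures.

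**3. What the responders-only reading can do.** All rates here are assumptions, and anyone who would respond on placebo is assumed also to respond on LY. Let rp and rl be Week 12 response on placebo and LY. Let a0 and a1 be Week 52 success on placebo and LY in patients who would respond on either arm, and i1 Week 52 success in patients who respond only on LY.

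- Responders-only difference = [rp·a1 + (rl − rp)·i1]/rl − a0
- mITT composite difference = [rp·a1 + (rl − rp)·i1] − rp·a0
- The first is negative when i1 < (rl·a0 − rp·a1)/(rl − rp)

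With rp = 0.20, rl = 0.50, a0 = 0.50, a1 = 0.60, i1 = 0.30:

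- Responders only: (0.12 + 0.09)/0.50 − 0.50 = 0.42 − 0.50 = −8 points
- Composite: 0.21 − 0.10 = +11 points
- Break-even i1: (0.25 − 0.12)/0.30 = 0.43

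| rp | rl | a0 | a1 | i1 | Responders only | Composite | Break-even i1 |
|---|---|---|---|---|---|---|---|
| 20% | 50% | 50% | 60% | 30% | −8 | +11 | 43% |
| 30% | 60% | 50% | 60% | 30% | −5 | +12 | 40% |
| 30% | 50% | 50% | 60% | 30% | −2 | +9 | 35% |
| 30% | 50% | 50% | 60% | 60% | +10 | +15 | 35% |

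For the first row, simulation with 40 placebo and 40, 60 or 80 LY patients gives an observed responders-only difference below zero in 63%, 64% and 65% of trials. For the composite the figures are 6.1%, 5.5% and 4.1%.

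**4. Precision.** Assume 20% to 35% of 40 placebo patients respond, which is 8 to 14 people. Half-width = 1.96 × √(0.25/n0 + 0.24/n1), taking Week 52 rates of 50% on placebo and 40% on LY.

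- n1 = 40 (80-patient arm, 50% response): 37.8 points at n0 = 8; 30.3 at n0 = 14.
- n1 = 20 (40-patient arm, 50% response): 40.8 points at n0 = 8; 33.9 at n0 = 14.

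The four CMH factors form 2 × 2 × 2 × 3 = 24 strata. With at most 14 placebo responders, at least 10 strata hold no placebo patient and add nothing to the test.

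**The case against.** The strongest reply is that Section 4.4.1.3 may already specify the composite. Its third condition cannot define a denominator, so the list may be meant as success criteria. Section 4.4.1.2 uses the same construction for Week 12, where the conditions are plainly success criteria over mITT, and SAP Section 1.1 also puts success criteria under the population label for the Week 12 secondary endpoints. This stands as a possible reading, so a reader should not infer that the plan definitely tests responders only. It does not settle the matter, because SAP Section 3 and the Week 52 NRI rule point the other way.

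A reader might also infer that the sign will reverse, or that a true maintenance benefit will be hidden. The documents do not support that. Reversal needs LY-only responders to hold their status less well than the break-even rate; at 60% the difference is +10 points. Nor is the composite a maintenance estimate: of its +11 points in the first row, 0.20 × (0.60 − 0.50) = 2 come from patients who would respond on either arm and 0.30 × 0.30 = 9 from LY-only responders. It could be positive with no maintenance effect at all. Placebo nonresponders also count as failures by rule, because they have moved to LY.

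Small numbers affect the composite too: in the first row with 80 LY patients, its half-width is 1.96 × √(0.21·0.79/80 + 0.10·0.90/40), about 13 points.

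Finally, these are secondary Phase 2 endpoints without multiplicity control. The primary analysis and the planned interim decisions rest on Week 12 data and are unaffected.

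**Conclusion.** What is firmly shown is a contradictory denominator for all eight Week 52 comparisons, with a literal wording that also conflicts with NRI. On one of the two workable readings, responders only, the tested difference is not protected by randomisation and should not be presented as a treatment effect of maintenance.

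Sign reversal is a possibility under stated assumptions (−8 against +11 points, only if LY-only responders succeed at less than about 43%), not a prediction. In other cases the estimate may keep its sign and still be distorted. The imprecision, about 30 to 38 points against 40 LY responders and 34 to 41 against 20, rests on assumed response rates. The point should be corrected before the Week 52 analysis, but it does not touch the primary conclusion.

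**What to change.** Reconcile Protocol Section 3 with SAP Sections 1.1, 3, 4.1.2.1 and 4.4.1.3. For each Week 52 endpoint, define the tested comparison as the proportion of all mITT participants who were Week 12 responders and who meet the endpoint at Week 52 without having discontinued. Everyone else in mITT counts as a failure. Take the Week 52 status conditions out of the population definition and put them in the endpoint definition, so that they agree with NRI.

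Label the result as a treat-through comparison, that is, durable response from baseline. Report rates among Week 12 responders descriptively, marked as non-randomised and without p-values.

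The cost is wording and one more table per endpoint from data already collected. There are two downsides. Percentages will be lower because the denominator is larger. The composite carries the induction effect, so it does not isolate a maintenance effect, which this design cannot do without re-randomisation at Week 12.

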4.4.2. Secondary Health Outcome Endpoints

The following are patient-reported outcome instruments collected using a participant eDiary:

- Rectal Bleeding
- Stool Frequency
- Nocturnal Stool
- Bristol Stool Scale

- Urgency NRS
- Abdominal Pain NRS
- Fatigue NRS, and
- PGR-S

The following are patient-reported outcome instruments collected electronically:

- PGI-C and
- IBDQ

Where appropriate, the total scores and sub-totals for individual dimensions collected will be summarized with means and 95% CIs by time point and by treatment group. The summary table will also include the change from baseline scores wherever applicable. The mean raw scores and mean change from baseline scores with corresponding 95% CIs will be presented graphically by treatment group and in a longitudinal fashion.

The ITT population will be used for all health outcome analyses

Mean change from baseline will be summarized by treatment group.

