Study day	99	113	127	141	155	169	183	197	211	225	
Visit interval tolerance (days)	±3	±3	±3	±3	±3	±3	±3	±3	±3	±3	
Fasting visit						X					
Diary compliance check	X	X	X	X	X	X	X	X	X	X	Check compliance for Stool Frequency Rectal Bleeding Nocturnal Stools Bristol Stool Scale Urgency NRS Abdominal Pain NRS Fatigue NRS, and Patient Global Rating of Severity (PGR-S).
Patient-Reported Outcomes (Electronic)											
Inflammatory Bowel Disease Questionnaire (IBDQ)						X					
Patient Global Impression of Change (PGL-C)						X					
QIDS-SR16						X					
Laboratory Tests and Sample Collections											
Hematology		X		X		X		X		X	
Clinical chemistry		X		X		X		X		X	

Table 2. Schedule of Activities for the Maintenance Treatment Period of Study J1P-MC-KFAH											
This schedule applies to study participants who are responders at Week 12.											
For procedures at an ETV, see ETV in Table 4.											
For procedures at an unscheduled visit, see V997 in Table 4.											
Visits 10 through 28 are eligible to be conducted remotely (that is, by telephone, IT-assisted virtual visit, mobile healthcare, or a combination thereof), if written approval is provided by the sponsor and according to the preferences of the participant and the study site. However, no more than 34 days can elapse without an on-site study visit occurring.											
Visit number	V10	V11	V12	V13	V14	V15	V16	V17	V18	V19	Comment
Weeks from randomization	14	16	18	20	22	24	26	28	30	32	
Study day	99	113	127	141	155	169	183	197	211	225	
Visit interval tolerance (days)	±3	±3	±3	±3	±3	±3	±3	±3	±3	±3	
Fasting visit						X					
Lipid panel						X					Fasting samples are preferred, but if participant is nonfasting at time of collection, this is not a protocol deviation.
Urinalysis		X		X		X					
Urine pregnancy (local)		X		X		X		X		X	Perform only for women of childbearing potential and women with a history of tubal ligation. At dosing visits which have pregnancy testing, the pregnancy test result must be confirmed to be negative prior to dosing. Pregnancy testing may be performed more frequently than designated on the SoA, if local laws or regulations require more frequent testing.
CCI						X					
HBV DNA						X					Only for participants who are positive for anti-HBc at screening.
Pharmacokinetic (PK) samples						X					Collect samples before dosing, if dosing is scheduled. Collect additional samples at specified times relative to onset of hypersensitivity events.

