For procedures at an unscheduled visit, see V997 in Table 4.											
Visits 17 through 28 are eligible to be conducted remotely (that is, by telephone, IT-assisted virtual visit, mobile healthcare, or a combination thereof) if written approval is provided by the sponsor and according to the preferences of the participant and the study site. However, no more than 34 days can elapse without an on-site study visit occurring.											
Visit number	V10	V11	V12	V13	V14	V15	V16	V17	V18	V19	Comment
Weeks from randomization	14	16	18	20	22	24	26	28	30	32	
Study day	99	113	127	141	155	169	183	197	211	225	
Visit interval tolerance (days)	±3	±3	±3	±3	±3	±3	±3	±3	±3	±3	
Fasting visit							X				
Diary compliance check	X	X	X	X	X	X	X	X	X	X	Check compliance for Stool Frequency Rectal Bleeding Nocturnal Stools Bristol Stool Scale Urgency NRS Abdominal Pain NRS Fatigue NRS, and Patient Global Rating of Severity (PGR-S).
Patient-Reported Outcomes (Electronic)											
Inflammatory Bowel Disease Questionnaire (IBDQ)							X				
Patient Global Impression of Change (PGI-C)							X				
QIDS-SR16							X				
Clinician-Administered Questionnaires (Paper)											
Physician’s Global Assessment (PGA)							X				

Table 3. Schedule of Activities for the Extension Induction and Extension Maintenance Treatment Periods of Study J1P-MC-KFAH											
This schedule applies to study participants who are nonresponders at Week 12.											
V16 procedures may be conducted over more than 1 day as long as all activities are completed within the allowable visit tolerance and all scheduled activities are completed prior to dosing											
For procedures at an ETV, see ETV in Table 4.											
For procedures at an unscheduled visit, see V997 in Table 4.											
Visits 17 through 28 are eligible to be conducted remotely (that is, by telephone, IT-assisted virtual visit, mobile healthcare, or a combination thereof) if written approval is provided by the sponsor and according to the preferences of the participant and the study site. However, no more than 34 days can elapse without an on-site study visit occurring.											
Visit number	V10	V11	V12	V13	V14	V15	V16	V17	V18	V19	Comment
Weeks from randomization	14	16	18	20	22	24	26	28	30	32	
Study day	99	113	127	141	155	169	183	197	211	225	
Visit interval tolerance (days)	±3	±3	±3	±3	±3	±3	±3	±3	±3	±3	
Fasting visit							X				
Laboratory Tests and Sample Collections											
Hematology	X	X	X	X	X	X	X	X		X	

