The CMH chi-square p-value and the relative risk along with its 2-sided CI will be provided. In addition, the absolute treatment difference in proportions will be provided along with the 2-sided CI estimate. The differences between each treatment group and placebo will also be tested separately using a logistic regression model that controls for at least previous advanced therapy failure status (yes/no) and corticosteroid use (yes/no). If deemed necessary, additional analyses of categorical efficacy variables may be conducted to address sparse data and/or small sample sizes.

Treatment comparisons of continuous efficacy and health outcome variables with multiple postbaseline time points will be made using MMRM analysis. The MMRM will include the following effects and covariates:

- treatment group
- previous advanced therapy failure status (yes/no)
- corticosteroid use (yes/no)
- disease activity (MMS: [4 to 6] or [7 to 9]) at baseline)
- region (North America/Europe/Other)
- baseline value in the model
- visit, and
- the interactions of treatment-by-visit and baseline-by-visit as fixed factors.

The covariance structure to model the within-participant errors will be unstructured. If the unstructured covariance matrix results in a lack of convergence, the heterogeneous Toeplitz covariance structure, followed by the heterogeneous autoregressive covariance structure, will be used. The first structure to yield convergence will be used for inference. The Newton-Raphson with ridging optimization technique will be used to aid with convergence. The Kenward-Roger

method will be used to estimate the denominator degrees of freedom. Type III sums of squares for the LS means will be used for the statistical comparison; the 95% CI will also be reported. Treatment group comparisons with placebo at Week 12 and all other appropriate time points will be tested.

Treatment comparisons of continuous efficacy and health outcome variables with a single postbaseline time point will be made using ANCOVA with the following in the model:

- treatment group
- previous advanced therapy failure status (yes/no)
- corticosteroid use (yes/no)
- disease activity (MMS: [4 to 6] or [7 to 9]) at baseline)
- region (North America/Europe/Other), and
- baseline value.

Type III sums of squares for LS means will be used for statistical comparison between treatment groups. The LS mean difference, standard error, p-value, and 95% CI, unless otherwise specified, will also be reported.

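### Between Weeks 12 and 52 the IBDQ is scheduled at Week 24 for responders and Week 26 for nonresponders, so by-arm all-randomised curves shift with who is measured

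*SAP*

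**What the plan says.** **Schedule.** Protocol Table 2 (Section 1.3.2) states: "This schedule applies to study participants who are responders at Week 12". Its only IBDQ and PGI-C between Weeks 12 and 52 are at V15, Week 24. Protocol Table 3 (Section 1.3.3) states: "This schedule applies to study participants who are nonresponders at Week 12". Its only ones in that interval are at V16, Week 26. All participants have the IBDQ at baseline and Week 12, and both tables have it at Week 52. The eDiary measures run in both tracks and are not affected.

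**Analysis.** SAP 4.4.2 asks for summaries by time point and treatment group and adds that "mean change from baseline scores with corresponding 95% CIs will be presented graphically by treatment group and in a longitudinal fashion". On the population it says: "The ITT population will be used for all health outcome analyses". SAP Section 3 defines ITT as "All randomized participants. Participants will be analyzed according to the treatment to which they were assigned". The PRO estimand in SAP 1.1 takes all patients with moderately to severely active UC as its population, for Weeks 12 and 52. SAP 4.1.1 assigns continuous outcomes with several postbaseline visits to an MMRM with treatment-by-visit terms. It specifies: "The covariance structure to model the within-participant errors will be unstructured". It also says: "Treatment group comparisons with placebo at Week 12 and all other appropriate time points will be tested".

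**Conflicting text.** The closing sentence of SAP Section 3 bases maintenance and extension analyses on whoever enrolled in the period concerned. The table it refers to defines no maintenance or extension set. No text merges Weeks 24 and 26, gives an IBDQ visit window, or puts Week 12 response status in the model.

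**The concern.** By schedule, Week 24 holds only responders, Week 26 holds only nonresponders, and nobody has both. A single by-arm curve through Weeks 12, 24, 26 and 52 therefore joins means from different people. It would rise and then fall without any individual changing, and an arm difference present at Week 12 could seem to disappear. Week 12 response is defined by the modified Mayo score, which is not in the IBDQ model as a post-baseline variable, so the missing-at-random assumption does not fully account for who is measured. The IBDQ is a named secondary measure, and a figure drawn as 4.4.2 prescribes could be read as a late gain followed by loss of effect.

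**Working it through.** **Plan's own figure.** There is none to reproduce. The documents give no IBDQ mean, SD or effect and no clinical response rate. Their power figures concern Week 12 remission and do not enter here. All inputs below except the schedule are assumptions.

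**1. Plotted means.** Let p be the Week 12 response proportion in an arm, mR the mean IBDQ change in responders and mN that in nonresponders. Both are taken as equal across arms and flat after Week 12.

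- Week 12 mean = p·mR + (1 − p)·mN
- Week 24 mean = mR (responders only)
- Week 26 mean = mN (nonresponders only)
- Week 12 arm difference = (p_LY − p_P)(mR − mN). At Weeks 24 and 26 it is 0.

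With p = 0.55 v 0.35, mR = 50 and mN = 15:

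| | Week 12 | Week 24 | Week 26 |
|---|---|---|---|
| LY3471851 | 0.55×50 + 0.45×15 = 34.25 | 50 | 15 |
| Placebo | 0.35×50 + 0.65×15 = 27.25 | 50 | 15 |
| Difference | 7.0 | 0 | 0 |

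The curves rise by 15.75 and 22.75 points and then fall by 35, although nobody has changed.

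**2. Range.**

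- Response 40% v 20%, gap mR − mN = 20: a Week 12 difference of 0.20×20 = 4.0 becomes 0.
- Response 60% v 30%, gap 35: 0.30×35 = 10.5 becomes 0.
- Response 40% in both arms: the difference stays at 0, but the curves still rise by 0.60×20 = 12 or 0.60×35 = 21.

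The trend artefact needs only that responders score better than nonresponders. The arm-difference artefact also needs response rates, or effects within response status, to differ by arm.

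**3. All-participant MMRM.** Maximum-likelihood fits of an arm-by-visit model with unstructured covariance were run on 20,000 simulated participants per arm, with SD 25 within response status and no change after Week 12.

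| Within-person correlation | Week 24 difference, 55% v 35% (true 7.0) | Week 24 difference, 60% v 30% (true 10.5) |
|---|---|---|
| 0.3 | 2.8 | 4.8 |
| 0.5 | 4.1 | 6.7 |
| 0.7 | 5.8 | 9.0 |

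Simulation error in the first column is about √(625/7,000 + 625/11,000) = 0.4; a repeat with another seed gave 2.8, 4.7 and 5.2. The model recovers part of the difference, and more as the correlation rises. In the 60% v 30% case the Week 52 difference was 10.2 to 10.3, beside 10.4 to 10.8 at Week 12.

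**4. Covariance.** Four visits give 4×5/2 = 10 covariance parameters. Under this schedule the information matrix has rank 9 of 10, and the element without data is Cov(Week 24, Week 26). Three starting values for that correlation ended at 0.00, 0.42 and 0.78 with the same log-likelihood (−394700.92) and the same LS means. If the flat direction upset convergence, the heterogeneous Toeplitz fallback would set corr(12,24) = corr(24,26) = corr(26,52), although the gaps are 12, 2 and 26 weeks.

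**The case against.** The best defence is that the SAP never says one fit spans both tracks. On the Section 3 reading, induction has one postbaseline IBDQ, which 4.1.1 sends to ANCOVA; maintenance has Weeks 24 and 52; and extension has Weeks 26 and 52. Neither problem then arises. That reading is available, but 4.4.2 and the PRO estimand point the other way and Section 3 defines no period sets, so the conflict stands.

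It is also fair that no Week 24 or Week 26 IBDQ test is named. The endpoints are changes to Week 12 and Week 52, and 4.1.1 refers only to appropriate time points. The longitudinal by-arm plot, however, is prescribed.

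A reader might infer that the unstructured matrix cannot be estimated, or that a fallback is forced. The documents do not support that. One element of ten lacks data, LS means do not depend on it, and no convergence or Kenward-Roger failure has been shown. The risk is only that it may disturb either and trigger a fallback structure. Nor does the arm difference always vanish: with equal response rates and equal effects within status it does not move.

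Pooling V15 and V16 as one by-arm visit looks like an easy remedy but is not clean, because nonresponders, including those randomised to placebo, receive LY3471851 from Week 14. For illustration, suppose placebo-arm nonresponders then gain 15 points and LY-arm nonresponders gain 5. The 7.0 difference becomes 7.0 + 0.45×5 − 0.65×15 = −0.5.

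QIDS-SR16 has the same visit split, but the SAP treats it as a safety measure outside 4.4.2, so it is not part of this point.

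**Conclusion.** The point holds for the post-Week 12 presentation of the IBDQ and PGI-C and for any all-randomised arm comparison at Week 24 or Week 26. Read with ITT, SAP 4.4.2 yields curves whose rise and fall reflect who was measured, and an arm difference that can go from 7.0 to 0 (4.0 to 10.5 falling to 0 over the unequal-rate cases tried). An MMRM leaves about 2.8 to 5.8 of a true 7.0 at Week 24. These sizes rest wholly on assumed response rates and IBDQ changes; the schedule split and the conflict over populations rest on the documents.

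A reader might infer that the named Week 12 and Week 52 comparisons are compromised. This mechanism does not do that: their LS mean differences were essentially unaffected in the simulations, which assumed no treatment effect after Week 12. The nonresponders' move to LY3471851 at Week 14 is a separate question for Week 52. The change should be made, since the prescribed output would mislead and correcting it is easy.

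**What to change.** 1. Reconcile SAP Section 3, the PRO estimand in SAP 1.1 and SAP 4.4.2 on which population applies after Week 12, and define the Maintenance and Extension sets.
2. In SAP 4.4.2, present post-Week 12 IBDQ and PGI-C summaries and curves separately for the Maintenance (responder) and Extension (nonresponder) tracks, with n at each point.
3. In SAP 4.1.1, list the IBDQ visits that are modelled and tested. Leave Weeks 24 and 26 out of the all-participant model, which also removes the covariance element without data. Analyse Week 24 within the Maintenance population and Week 26 descriptively within the Extension population.
4. Do not pool V15 and V16 as one by-arm visit without stating what nonresponders in every arm receive from Week 14.

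The cost is SAP wording, with no new data. The downside is that post-Week 12 comparisons are conditional on Week 12 response, so they are not comparisons of the groups as randomised and must be labelled accordingly.
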